Screening/baseline visit will include study screening, informed consent, and initial study questionnaires and specimen collections. At this visit, enrolled Participants will be provided with 8 weeks of hydroxychloroquine (HCQ) or placebo pills based on their randomized study group.

Participants will be asked to contact the study team if COVID-19 infection is established at any time during the study. For study weeks 1,2,3,5,6 &7, Participants will receive a monitoring questionnaire to assess for COVID-19 symptoms/diagnosis, adherence and medication side effects. These monitoring visits will be done by telephone and/or electronic encounters (virtual visits, email), whichever method the patient prefers to encourage adherence to the monitoring. Every effort will be made to obtain the weekly information from Participants and avoid missing timepoint information. Participants will have a +/- 3 day window to complete their scheduled study visits. As recommended in the FDA Guidance on Conduct of Clinical Trials of Medical Products during the COVID-19 Pandemic, updated on March 27, 2020, the approach of using electronic or virtual visits for study safety assessments will support study monitoring while increasing the safety for participants by reducing potential exposures to SARS-COV-2 while attempting to come to clinical areas for study visits, where no direct contact is needed as part of trial design.

The study Participant will have an in-house, face-to-face visit on week 4 of the study to obtain monitoring questionnaires to assess for COVID-19 symptoms/diagnosis, adherence and medication side effects, and collect study blood samples. At study week 8, participants will present for the final study visit and will provide additional samples of whole blood, as well as complete an end of study questionnaire. Participants who are determined to be positive for

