6.3 Study Aims, Hypothesis and Proposed Analysis

6.3.1 Primary Aim and Hypothesis

As noted below, the primary aim has been changed to: (based on Study Protocol dated 05/26/2020)

To determine if the use of hydroxychloroquine as preventive therapy decreases the rate of acquisition of SARS-CoV 2 infections [with clinical COVID-19 disease](#) in Study Participants [for each randomized treatment arm](#) as compared to placebo.

From: (based on original Study Protocol, dated at and after 04/06/2020)

To determine if the use of hydroxychloroquine as preventive therapy decreases the rate of acquisition of SARS-CoV 2 infections in Study Participants as compared to placebo.

Primary Hypothesis (P1): Hydroxychloroquine administered daily decreases the rate of acquisition of SARS-CoV 2 infections with clinical COVID-19 disease, compared to placebo; and hydroxychloroquine administered weekly decreases the rate of acquisition of SARS-CoV 2 infections with clinical COVID-19 disease, compared to placebo.

The **primary outcome** will be defined as clinical COVID-19 disease with laboratory confirmation of infection.

Presentation with COVID-19 symptoms during study follow-up (defined as fever $\geq 38^{\circ}$ C, or two or more non-fever symptoms that are new since the baseline) will refer participants to obtain SARS-CoV 2 testing through employee health or participants' primary care physician, with test results documented in their medical record.

Laboratory confirmation of SARS-CoV 2 infection (SARS-CoV 2 test positive) will be defined as at least one positive RT PCR, or both IgM and IgG positive serology. The lab test results can be obtained from (a) study blood samples (IgM and IgG serology), and (b) RT PCR test results ordered by a participant's primary care physician or through employee health.

All participants who test SARS-CoV 2 positive will be followed for at least 30 days after the first positive test for presentation of symptoms.

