6.3.2 Full Analysis Set (FAS)

All randomized subjects who do not have a SARS-CoV 2 positive test at the baseline, have taken at least one dose of study medication and provide at least one post-baseline follow-up during the 8-week treatment period. Participants will be analyzed according to the treatment group to which they were assigned according to Intention to treat (ITT).

6.3.3 Safety Analysis Set:

The safety analysis set will consist of all subjects randomized who receive at least one dose of study medication.

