To address this, we will conduct Tipping Point Analysis (TPA) under the condition of missing not at random (MNAR) to assess the robustness of the primary analysis. Specifically, the TPA first step (STEP 1) is to conduct m (e.g., $m=5$ or 10) multiple imputation (MI) based on baseline covariates, and the prior to 8-week and post-baseline covariates to estimate the missing primary binary endpoint (D) with the underlying assumption of MAR. We will use the Markov Chain Monte Carlo (MCMC) algorithm based on the assumption of multivariate normality (Schafer 1997, Allison 2001) for estimating the mean of D (Allison 2017) stratified by treatment group without rounding to binary values. However, this approach is still under the MAR assumption and hence the result will be further examined by shifting the imputed mean of D in a range of negative to positive values, which can be done by inflecting or suppressing the mean of D among those who had missing D in treated group. A tipping point is identified if it reverses the study conclusion. Those results will be further evaluated on whether the imputed value associated with the tipping point is plausible. SAS Procedures PROC MI and PROC MIANALYZE and SAS %midata macro can be used for TAP analysis.

Sensitivity Analysis #2: A control-based MI

For the most conservative approach, MI can be restricted using data only from the placebo group for the missing endpoint D in both the treated and placebo groups using a similar approach described above for the sensitivity analysis #1 with the shift=0 (the first step).

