6.3.4.4 Secondary Aims, Hypotheses and Analyses

S1: To compare the rates of SARS-CoV 2 infection status between the randomized treatment arms and the control arms to determine the effect of HCQ dose in the prevention of COVID-19 viremia and disease.

Secondary Hypothesis (S1): There is a hydroxychloroquine dose effect on acquisition of SARS-CoV 2 infection status, compared to placebo.

The endpoint will be SARS-CoV 2 infection status, defined as 1) no SARS-CoV 2 test positive during study follow up; 2) SARS-CoV 2 test positive (i.e., at least one positive RT PCR, or both IgM and IgG positive serology) without clinical symptoms (“asymptomatic SARS-CoV 2 test positive”) 3) SARS-CoV 2 test positive with clinical symptoms (“symptomatic SARS-CoV 2 test positive”).

The analysis will be conducted using FAS. Ordinal logistic regression will be used and analysis will start testing the overall daily and weekly dose effect, followed by pairwise/subgroup comparisons if an overall dose effect is detected at 0.05 level.

S2: To compare the rates of SARS-CoV 2 infection status in the non-randomized comparator arm to the randomized groups to assess the impact of chronic weight-based dosing of HCQ for COVID-19 prevention.

Secondary Hypothesis (S2): There is weekly /daily HCQ dose effect on acquisition of SARS-CoV 2 infection, compared to patients who were already on HCQ.

The endpoint will be the same as described for S1. The analysis will include all randomized *in FAS and non-randomized study participants with at least one post-baseline follow-up.*

We will first test for treatment selection bias using the data collected at the baseline. Inverse probability treatment weighting (IPTW)/propensity score, or matched sub-cohort will be considered to adjust for imbalanced participant characteristics. A similar analysis to that of S1 will be used for testing hypothesis S2.

S3: To compare the rate of SARS-CoV 2 infections as measured by serum IgM/IgG in participants receiving HCQ versus placebo.

Secondary Hypothesis (S3): There is weekly /daily dose effect on status of SARS-CoV 2 infection as measured by serum IgM/IgG, compared to placebo.

The endpoint will be serum IgG/IgM status at each participant’s study conclusion, classified as:

1. Negative (consistently negative for both serologies)
2. Indeterminate (IgM positive, with IgG consistently negative)
3. Positive (IgM and IgG positive, or IgG positive)

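### S1 and S2 count participants with no post-baseline test as uninfected, which biases the comparison toward HCQ if more HCQ participants go untested

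*SAP*

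**What the plan says.** S1 in SAP 6.3.4.4 has three ordered levels. The definition opens with the lowest: "The endpoint will be SARS-CoV 2 infection status, defined as 1) no SARS-CoV 2 test positive during study follow up". The other two each need a positive test, without or with symptoms. No level exists for participants who were not tested, and no rule says when S1 status is missing. On the analysis the SAP says: "The analysis will be conducted using FAS. Ordinal logistic regression will be used". S2 takes over the same endpoint and adds the non-randomized comparator group, whose members also enter on a single follow-up.

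To enter the FAS (SAP 6.3.2) a participant must have no positive baseline test, take one dose and "provide at least one post-baseline follow-up during the 8-week treatment period". No post-baseline test is required. Protocol section 4 makes weeks 1, 2, 3, 5, 6 and 7 remote: "These monitoring visits will be done by telephone and/or electronic encounters (virtual visits, email), whichever method the patient prefers".

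On where test results come from, SAP 6.3.1 says: "The lab test results can be obtained from (a) study blood samples (IgM and IgG serology), and (b) RT PCR test results". Referral for PCR follows symptoms. Post-baseline study blood is drawn at weeks 4 and 8 (Protocol 7.3).

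On missing data, SAP 6.3.4.2 sets an observed-data analysis under missing at random (MAR). The imputation steps in SAP 6.3.4.3 are there "to estimate the missing primary binary endpoint (D) with the underlying assumption of MAR". Protocol 6.3 counts early withdrawals as positive when their clinical disease status cannot be confirmed. By contrast, the negative category in S3 is worded as serology results that were actually negative.

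**The concern.** Level 1 is satisfied by having no result at all. PCR is prompted by symptoms, so an infection without symptoms is found mainly in the week-4 or week-8 blood. Someone who answers the week-1 email and then gives no blood stays in the FAS and, if symptom-free with no clinical PCR, is counted as uninfected.

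This matters only if the untested share differs between arms. That is plausible: Protocol 10.3 lists nausea, vomiting, dizziness and visual effects for HCQ, and Protocol 6.3 says that participants who withdraw consent, are lost or are taken off study are not approached again. If more HCQ participants leave before giving blood, fewer of their asymptomatic infections are seen. S1 could then show a dose effect on infection when the drug does nothing.

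**Working it through.** **Plan's own figure.** SAP 6.4 points to correction method #3 (combined HCQ arms against placebo, one test) for S1 with a binary endpoint, and gives power 0.835 at 935 per arm for 10% v 6.8%. Pooled rate (0.10 + 2×0.068)/3 = 0.0787. Null SE = √[0.0787×0.9213×(1/935 + 1/1870)] = 0.01078. Alternative SE = √[0.10×0.90/935 + 0.068×0.932/1870] = 0.01141. z = (0.032 − 1.96×0.01078)/0.01141 = 0.95, so power is 0.830. At 900 per arm the same steps give 0.816 against the stated 0.819. Both agree closely; the power figure is not in dispute, and the same two-group layout is used below.

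**Inputs**
- 935 per arm, so 935 placebo v 1,870 HCQ; two-sided 0.05 (SAP 6.4 and S1).
- π, true infection rate, equal in all arms (no drug effect). The protocol background cites 10–30% of healthcare workers.
- a, share of infections found only by study serology. The background gives up to 85% asymptomatic or minimally symptomatic. Taking π = 20% and a = 50% gives 0.20×0.50 = 10% symptomatic infection, which matches the 10% clinical disease planned for placebo.
- u, share with neither post-baseline draw, so that their asymptomatic infections go unseen. The documents give no value. Assumed: 5% on placebo; 5, 10, 15 or 20% on HCQ.

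**Formula.** Symptomatic infections are found by PCR whatever happens to the blood; asymptomatic ones only if blood is given. The observed positive rate in an arm is π(1 − a·u). For π = 20%, a = 50%, u = 15%: 0.20×(1 − 0.075) = 18.5%, against 0.20×(1 − 0.025) = 19.5% at u = 5%; ratio 0.949.

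**Results at π = 20%.** A false benefit is a significant result in favour of HCQ (nominal 2.5%). Rates come from 40,000 simulated trials per setting, using the tie-corrected rank-sum test, which is the score test of the proportional-odds model.

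| Untested, placebo v HCQ | a = 50%: observed rates | Ratio | False benefit | a = 85%: observed rates | Ratio | False benefit |
|---|---|---|---|---|---|---|
| 5% v 5% | 19.5 v 19.5% | 1.00 | about 2.5% | 19.15 v 19.15% | 1.00 | about 2.5% |
| 5% v 10% | 19.5 v 19.0% | 0.97 | about 5% | 19.15 v 18.3% | 0.96 | about 8% |
| 5% v 15% | 19.5 v 18.5% | 0.95 | about 8% | 19.15 v 17.45% | 0.91 | about 19% |
| 5% v 20% | 19.5 v 18.0% | 0.92 | about 14% | 19.15 v 16.6% | 0.87 | about 37% |

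If symptom-driven PCR finds every infection (a = 0), the ratio is 1.00 whatever the untested shares.

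**What other scoring rules do** (π = 20%, a = 50%, 5% v 15% untested)
- *Drop untested non-positives.* PCR positives stay in, so the evaluable share is 1 − u×0.90, that is 0.955 v 0.865. Rates are 0.195/0.955 = 20.4% v 0.185/0.865 = 21.4%; ratio 1.05, now against HCQ.
- *Impute within those without a positive PCR.* They are 90% of each arm, and 0.10/0.90 = 11.1% of them are infected. If attendance is unrelated to infection within this group, both arms recover 0.10 + 0.90×0.111 = 20%; ratio 1.00.
- *Count every untested participant as positive*, which is Protocol 6.3 stretched to S1: 0.20×0.95 + 0.05 = 24% v 0.20×0.85 + 0.15 = 32%; ratio 1.33.

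**The case against.** The strongest reply is that SAP 6.3.4.2 already limits efficacy analyses to observed data under MAR, so an untested participant is simply missing. That would settle the matter if S1 left such a participant without a value. It does not: the definition gives them level 1, and nothing in 6.3.4.2 overrides it. Protocol 6.3 does not help either. It concerns clinical disease status, is not repeated in the SAP, and points in the opposite direction.

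Several other objections stand in part:
- A reader might infer that any arm with more missed draws will look protected. The documents do not support that. There are two post-baseline draws, and Protocol section 9 adds record review for routine-care tests. One missed draw does not leave a participant untested.
- A reader might extend the point to S9, which also takes its endpoint from S1. But S9 uses week-4 and week-8 drug levels as covariates. A participant who gave neither sample lacks both and would largely fall out of that model.
- The 85% figure is an upper value that includes minimally symptomatic infection, and some of those people would meet the referral rule for PCR. At 20% infection it implies only 0.20×0.15 = 3% symptomatic disease, well below the planned 10%.
- The gap in testing is assumed. Protocol 10.3 describes the daily dose as about half the usual autoimmune dose and less likely to cause side effects. With a 5-point gap the effect is small.
- S3 offers a serology comparison with a properly worded negative category. It does not repair S1 or S2.

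**Conclusion.** The point holds for S1 and S2. As written, a symptom-free participant with no clinical PCR and no post-baseline blood is scored uninfected, and neither the observed-data rule nor the imputation planned for the primary endpoint corrects this. The bias favours HCQ only if the untested share is larger on HCQ.

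Its size is conditional. In the setting that matches the planned 10% clinical disease, the ratio moves from 1.00 to between 0.97 and 0.92 and the false-benefit rate from 2.5% to between about 5% and 14%, for untested gaps of 5 to 15 points. The rates of about 8–37% need the protocol's upper asymptomatic figure and should be read as an upper range, not an expectation. The documents do not show that testing will in fact differ by arm. They leave S1 unprotected if it does. S1 is secondary, but it is the first-listed comparison of infection itself, so the wording is worth correcting before database lock.

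**What to change.** In S1 and S2, define level 1 as no positive test plus an evaluable study-conclusion serology that does not meet the test-positive rule. A participant with no positive test and no such sample has missing status.

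Impute missing status by arm with a logistic or ordinal model that includes weekly symptom history, clinical PCR results and any week-4 serology. Complete-case analysis is not enough, because it over-retains PCR positives (ratio 1.05 above). The unrounded multivariate-normal method planned for the primary endpoint does not suit a three-level outcome. Add the delta (tipping-point) step, and tabulate post-baseline testing completeness by arm.

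State how this rule relates to the observed-data sentence in SAP 6.3.4.2 and the worst-case rule in Protocol 6.3, so that one treatment of untested participants applies to S1 and S2.

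The cost is SAP wording, some additional imputation code and slightly wider intervals. Participants with a negative week-4 sample but no week-8 sample also become missing; their week-4 result still informs the imputation.

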### **4. STUDY DESIGN**

The study will randomize a total of 3,000 HCW, FR, and DDOT bus drivers, age 18 to 75 years, through the Henry Ford Health System, Detroit COVID Consortium. HCW and NHW will include providers at both hospital/clinical settings and nursing homes. FR will include personnel working in both governmental, private or volunteer first responder services. DDOT bus drivers with the Detroit Department of Transportation. The participants who meeting study entry criteria and are not on HCQ prior to study enrollment will be randomized in a 1:1:1 blinded comparison of daily or weekly hydroxychloroquine versus placebo for 8 weeks.

A fourth non-randomized comparator group will be enrolled in the study comprising of HCW who are chronically on HCQ as part of their standard of care for their autoimmune disease(s). This will be an open enrollment group and will provide information of chronic weight-based daily therapy of HCQ effectiveness as a prophylactic/preventive strategy. These participants will continue on their therapy for the duration of the study.

The trial has implemented a pragmatic, adaptive enrichment design, where the efficacy analysis will be performed based on patients with negative screen for COVID-19 related symptoms at the baseline

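### The S2 hypothesis compares the randomised HCQ doses with chronic HCQ, so it does not answer its own prevention aim; chronic HCQ versus placebo should be the named contrast

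*SAP*

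**What the plan says.** Protocol section 4 gives the purpose of the fourth arm: it "will provide information of chronic weight-based daily therapy of HCQ effectiveness as a prophylactic/preventive strategy". The S2 aim in SAP 6.3.4.4 compares this arm with the randomised groups "to assess the impact of chronic weight-based dosing of HCQ for COVID-19 prevention".

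The S2 hypothesis takes a different reference: "There is weekly /daily HCQ dose effect on acquisition of SARS-CoV 2 infection, compared to patients who were already on HCQ". The S1 hypothesis, by contrast, is "There is a hydroxychloroquine dose effect on acquisition of SARS-CoV 2 infection status, compared to placebo". S3, S4, S6 and S7 also name placebo as the reference.

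For the S2 data, "The analysis will include all randomized" participants in the FAS, together with comparator participants who have post-baseline follow-up. Placebo is therefore in the dataset. For confounding, inverse probability weighting, a propensity score or a "matched sub-cohort will be considered to adjust for imbalanced participant characteristics". For the test itself, "A similar analysis to that of S1 will be used for testing hypothesis S2". The S1 analysis is an ordinal logistic regression that starts with an overall dose test, "followed by pairwise/subgroup comparisons if an overall dose effect is detected at 0.05 level". The SAP lists no S2 contrasts.

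**The concern.** Whether chronic HCQ prevents infection is a comparison of chronic HCQ with no HCQ, and placebo is the only arm without HCQ. The hypothesis as worded compares HCQ with HCQ. Its null, that the weekly and daily doses equal chronic dosing, covers two opposite states of the world: equal protection at every dose, and no protection at any dose.

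The contrast that would separate these states is possible within S2 but is not written down. SAP 6.3.4.1 classes analyses that the SAP does not describe, and that are run after database lock, as post hoc and exploratory. The status of an unnamed chronic-versus-placebo comparison would therefore be open to dispute. The S1 gate could also keep it from being reported at all. Neither P1 nor S1 includes the chronic arm, so S2 is the only prevention analysis across infection status that uses it against a reference group.

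**Working it through.** **Inputs from the documents.** 935 per randomised arm, placebo rate 10%, HCQ rate 6.8%, two-sided 0.05 (SAP 6.4).

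**Assumptions.**
- The comparator size is not stated; SAP 1.4 says only that it should be smaller than the randomised groups. A range of 100 to 900 is used.
- The 10% and 6.8% rates are planning rates for the primary endpoint and are borrowed for S2.
- The three-level S2 endpoint is collapsed to infected yes/no.
- No confounding and no weighting.

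**1. The plan's own figure.** SAP 6.4 gives no power for the comparison with the chronic arm. It ties its power remark on S1–S4 to Correction Method #3, daily plus weekly versus placebo, with stated power 0.835 at 935 per arm (Haybittle-Peto table, both HCQ rates 6.8%). The formula is

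power = Φ[(p0 − p1 − 1.96·se0)/se1],

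with se0 = √[p̄(1−p̄)(1/n0+1/n1)] and se1 = √[p0(1−p0)/n0 + p1(1−p1)/n1].

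Here p̄ = (93.5+127.16)/2805 = 0.0787, se0 = 0.01078 and se1 = 0.01141. Power = Φ[(0.032 − 0.02113)/0.01141] = Φ(0.952) = 0.830, which agrees with 0.835 within a point. This test contains no chronic-arm participants.

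**2. The hypothesis as worded.** Chi-square test (2 df) of weekly = daily = chronic; 200,000 simulated trials per setting.

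| Comparator n | No effect (all 10%) | Equal effect (all HCQ 6.8%) | Only chronic works | Only randomised doses work |
|---|---|---|---|---|
| 100 | 0.049 | 0.049 | 0.104 | 0.209 |
| 200 | 0.050 | 0.049 | 0.211 | 0.317 |
| 300 | 0.050 | 0.050 | 0.318 | 0.411 |
| 500 | 0.051 | 0.049 | 0.492 | 0.558 |
| 900 | 0.050 | 0.050 | 0.712 | 0.737 |

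The second and third columns are the same. The test also rejects when chronic HCQ is inert and only the randomised doses work.

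**3. A four-group overall test with placebo included** (3 df, same simulations).

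| Comparator n | No effect | All HCQ works | Randomised doses work, chronic inert |
|---|---|---|---|
| 100 | 0.050 | 0.693 | 0.724 |
| 200 | 0.050 | 0.701 | 0.750 |
| 300 | 0.050 | 0.710 | 0.770 |
| 500 | 0.050 | 0.724 | 0.805 |
| 900 | 0.050 | 0.748 | 0.855 |

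This gate does detect that HCQ works somewhere, but it rejects at least as often when chronic HCQ is inert. The signal comes mainly from the randomised arms. With 900 instead of 935 per randomised arm, the last two columns run from about 67% to 73% and 71% to 84%.

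**4. Chronic HCQ versus placebo.** Same formula with n0 = 935. For a comparator of 300: p̄ = (93.5+20.4)/1235 = 0.0922, se0 = 0.01920, se1 = 0.01754. Power = Φ[(0.032 − 0.03763)/0.01754] = Φ(−0.321) = 0.374.

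| Comparator n | Power, formula | Power, simulation |
|---|---|---|
| 100 | 0.14 | 0.141 |
| 200 | 0.27 | 0.274 |
| 300 | 0.37 | 0.382 |
| 500 | 0.53 | 0.536 |
| 900 | 0.69 | 0.698 |

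When chronic users have the placebo rate, this contrast rejects about 5% of the time, so it separates the two answers to the aim. The 95% interval half-width, 1.96·se1, is 1.96 × 0.0270 = 5.3 points at n = 100 and 1.96 × 0.0129 = 2.5 points at n = 900, against an assumed difference of 3.2 points.

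**The case against.** A reader might infer that S2 never tests the prevention question. The documents do not support that. The S2 aim and Protocol secondary endpoint 2 compare the chronic arm with the randomised groups, and Protocol 8.3 plans comparisons of that arm with the randomised arms. Placebo is one of them. It is in the S2 analysis set, and an S1-type analysis allows pairwise tests. Chronic versus placebo is within scope; what is missing is its name and its standing.

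A reader might also take 5% as the rejection rate of the S2 test under equal protection. That figure depends on reading the overall test as the worded hypothesis. The SAP does not define the S2 overall test, and a four-group test fits the stated analysis set. That part of the objection stands, but it does not rescue the plan, because the four-group test does not isolate chronic dosing either.

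The chronic-versus-randomised-dose comparison has a documented purpose: the Protocol synopsis and SAP 1.1 and 6.1 say the group is there for comparison with the randomised arms. So the hypothesis serves part of the arm's purpose and should be kept. Nor is an S2 result uninformative. Read alongside P1 and S1, it is indirect evidence on chronic dosing.

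Finally, the added contrast may be imprecise, and comparator participants have autoimmune disease. Both are true. They are reasons to report an interval and label the contrast properly, not to leave it unnamed.

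**Conclusion.** The point holds as a mismatch between a stated aim and its stated hypothesis. The logical part needs no assumed rates: the worded null is true under equal protection and under no effect. The rejection rates rest on the borrowed planning rates, the collapsed endpoint, the assumed comparator size and the absence of confounding. Weighting would generally reduce precision. Confounding could move the rejection rates in either direction, so the figures should not be read as upper limits.

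This concerns one non-randomised secondary aim. It does not touch the primary analysis or conclusion. It is still worth correcting, because prevention is the stated reason for enrolling the fourth arm. It would be wrong to dismiss it on the ground that S2 is exploratory: SAP 6.3.4.1 treats the analyses it describes as defined in advance.

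**What to change.** In SAP 6.3.4.4:

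- Restate the S2 hypothesis so that it names chronic HCQ versus the randomised placebo arm, adjusted by the weighting or propensity method already planned.
- Report that estimate with its confidence interval whatever the result of the overall test.
- Keep weekly versus chronic and daily versus chronic as separate dose comparisons, and state that non-significance there is not evidence of equal protection.
- Describe the chronic-versus-placebo contrast as non-randomised and open to confounding in either direction.
- State the expected comparator size and the precision it gives.

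The cost is a few sentences and one more contrast from the same adjusted model, with no new data. The drawback is that the interval may be too wide to settle the question if the comparator arm is small, and the text should say so in advance.
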